**Note: Everyone obtaining consent must complete [CITI training](#).**

**9.4 Will all subjects consent for themselves?**

- Yes If yes, adults lacking capacity to consent must be listed in the exclusion criteria (question 4.7).
- No If no, indicate below who, when appropriate, will provide consent
- Parent/guardian
- Legally authorized representative – **Appendix I required**

**9.5 What questions will be asked to assess the subjects' understanding? Questions should be open-ended and go beyond requiring a yes/no response.**

What are the benefits and risks of the tap or infiltration?

What are the benefits and risks of either local anesthetic medication?

How will your pain be managed post-operatively in both options of the study?

What are the alternative treatment options to control your pain post-operatively?

What will be done if you have an allergic reaction or reaction to the pain medication in this study?

**9.6 Participation in research must be voluntary. Describe the steps taken to minimize the possibility of undue influence on potential subjects.**

As the intervention we are providing two options which is the current standard of care, it is considered safe and efficacious. We will discuss the options, as well as the risks and benefits with the patient. No additional benefit is gained by the anesthesiologist if this technique is used and this will be discussed with the patient.

**Care of Subjects in Case of Accident**

*If this research involves a potential for injury, injury compensation language must be included in the consent form (see 21 CFR 50.25). If a contract to pay for research-related injuries exists, the language in the consent form should not contradict the language in the contract.*

9.7 Is there a potential for research related injury?

No If no, go to question 9.8  
 Yes If yes, indicate which of the following statements is included in the consent form

**Non-Sponsor Funded Compensation**

In the event that this research activity results in an injury, treatment will be available, including first aid, emergency treatment and follow-up care as needed. Care for such injuries will be billed in the ordinary manner, to you or your insurance company. If you think that you have suffered a research related injury let the study physicians know right away.

**Sponsor Funded Compensation**

In the event that this research activity results in an injury, treatment will be available, including first aid, emergency treatment and follow-up care as needed. Care for such injuries will be billed in the ordinary manner, to you or your insurance company. The sponsor of the study has some funds available to pay for care for injuries resulting directly from being in this study. If you think that you have suffered a research related injury and that you may be eligible for reimbursement of some medical care costs, let the study physicians know right away.

**If the preferred injury compensation language is unacceptable to the study sponsor, the following alternative language may be used:**

Under some circumstances the sponsor of the study will pay for care for injuries resulting directly from being in the study. If you want information about those circumstances or if you think you have suffered a research related injury let the study physicians know right away.

**Waiving Documentation of Consent**  
*Waiving written documentation assumes that there will be an informed consent process but signatures will not be collected on the consent form. The IRB may waive the requirement for written documentation under specific conditions.*

**9.8 Does the researcher wish to waive documentation of consent?**

No If no, go to question 9.9  
 Yes If yes, check the statement below that applies to justify waiving documentation of consent. If neither statement applies, researcher may not request waiver of documentation

- The only record linking the subject and the research would be the consent form and the principal risk of the research would be the potential harm from a breach of confidentiality (the IRB may allow an option to sign or decline)
- The research presents no more than minimal risk and includes no procedures for which written consent is normally required outside the research context.

NOTE: Researchers requesting a waiver of documentation must submit a consent form without signature lines with the IRB application.

**Waiving Consent**  
 The IRB may, in some **rare and specific** circumstances, waive the requirement for consent in accordance with 45 CFR 46.116(d). Answer the questions below to determine if waiver of consent may be considered.

**9.9 Does the researcher wish to waive consent?**

- No If no, go to section 10 - Funding  
 Yes Indicate if the following statements apply

	
The research involves no more than minimal risk to subjects.
 
 Yes   No – waiver may not be requested

	
Granting a waiver will not adversely affect the rights and welfare of the subjects.
 
 Yes   No – waiver may not be requested

	
The research could not practically be carried out without a waiver or alteration.
 
 Yes   No – waiver may not be requested
 
If consent is waived, whenever appropriate the subjects will be provided with additional pertinent information after participation. Describe below the process for providing subjects with this information.

**Section 10 Funding**

**10.1 Has funding for this project been applied for, requested or received or do you intend to request/apply for funding?**

- No Explain how the research will be conducted without funding:  
  
 YES Indicate in the table below who will provide/manage funds.

Funds provided/managed by	Required Supplemental Materials
 Internal University of Minnesota (departmental funds, internal grant program, etc.) Describe: Anesthesiology funds	none
 University of Minnesota Sponsored Project Funding	Appendix A required
 Non-University of Minnesota source or management	Appendix A required

**Section 11 Conflict of Interest**

Federal Guidelines emphasize the importance of assuring there are no conflicts of interest in research projects that could affect the welfare of human subjects. Reporting of financial interests is required from all individuals responsible for the design, conduct or reporting of the research. If this study involves or presents a potential conflict of interest, additional information will need to be provided to the IRB.

Examples of conflicts of interest may include, but are not limited to:

- A researcher participating in research on a technology, process or product owned by a business in which the researcher or family member holds a significant financial interest or a business interest.

- A researcher participating in research on a technology, process or product developed by that researcher or family member.
- A researcher or family member assuming an executive position in a business engaged in commercial or research activities related to the researcher's University responsibilities.
- A researcher or family member serving on the Board of Directors of a business from which that member receives University supervised Sponsored Research Support.
- A researcher receiving consulting income from a business that funds his or her research.
- A researcher receiving consulting income from a business that could benefit from the results of research sponsored by a federal agency (i.e. NIH).

**11.1 Do any of the Investigators or personnel listed on this research project have a business interest or a financial interest of \$10,000 or more (\$5,000 or more if research is funded by a Public Health Service (PHS) agency or researcher is involved in clinical health care) associated with this study when aggregated for themselves and their family members?**

No

Yes List the investigator(s) with conflicts:

[name] is on speakers bureau, consultant and has received research funds

**11.2. Do any of the investigators or personnel (when aggregated for themselves and their family members) listed on this research have:**

**11.2.1 Ownership interests more than \$10,000 (\$5,000 if research is funded by PHS or researcher is involved in clinical health care) when the value of interest could be affected by the outcome of the research?**

No

Yes List the investigator(s) with conflicts:

**11.2.2 Ownership interests exceeding 5% interest in any one single entity (or any equity interest in a non-publicly traded entity if research is funded by PHS or researcher is involved in clinical health care)?**

No

Yes List the investigator(s) with conflicts:

**11.2.3 Compensation greater than \$10,000 (\$5,000 if research is funded by PHS or researcher is involved in clinical health care) when the value of the compensation could be affected by the outcome of the research?**

No

Yes List the investigator(s) with conflicts:

**11.3 Have all business or financial interests indicated above been reported?**

- No
- Yes
- N/A There are no conflicts of interest on this study

- University of Minnesota researchers need to report business or financial interest online via the [Report of External Professional Activities \(REPA\)](#)
- Fairview Health System researchers need to complete the [Fairview Health Services Conflict of Interest Disclosure forms](#) and submit the completed forms to the Fairview Office of Research.
- Gillette Children’s Specialty Healthcare researchers must contact the Director of Research Administration, at [contact].

The IRB will verify that a management plan is in place with the Conflict of Interest (COI) Program. If the COI Program does not have an approved management plan in place for this research, they will contact the individual(s) for additional information.

Final IRB approval cannot be granted until the IRB has reviewed the management plan and all potential conflict matters are settled. The IRB receives a recommendation from the Conflict of Interest Review Committee regarding disclosure to subjects and management of any identified conflict. The convened IRB determines what disclosure language should be in the consent form.

**Section 12 Research Services, Assessment and Oversight**

**Section 12.1 RESEARCH COLLABORATIONS**

**12.1 Does this research project involve collaborations with any sites or personnel outside of the University of Minnesota, its coordinate campuses, the Fairview Health Systems or Gillette Children’s Specialty Healthcare?**

- No Go to question section 12.2
- Yes **Briefly describe the collaboration (with whom and for what purpose):**

Additional requirements for ensuring appropriate IRB oversight may apply. These requirements are often dependent on whether or not the site/personnel is considered “engaged” in human subjects research according to federal definitions. Contact the UMN IRB office ([[contact]](mailto:[contact])) to determine how IRB oversight of the research activity with the external site/personnel should be address.

**Section 12.2 AFFILIATED ENTITIES WITH OVERSIGHT RESPONSIBILITIES**

**12.2.1 Will this research use services, resources, or funding from the Clinical and Translational Science Institute?** Examples include pilot funding, career development awards, biostatistics support, facilities, staffing, project management, regulatory assistance, or informatics consultation and support

- No **Go to question 12.2.2**

Yes      **Provide CTR Portal ID#:**

**12.2.2 Does this research require [Masonic Cancer Center Protocol Review Committee \(CPRC\)](#) review?**

The CPRC is required to evaluate, approve or reject, monitor, and re-review on an annual basis all University of Minnesota clinical cancer research protocols including those with non-therapeutic intent.

No      **Go to question 12.2.3**

Yes      Documentation of approval must be provided to receive final IRB approval.

**12.2.3 Will this research utilize Gillette Children’s Specialty Healthcare resources or medical records?**

No      **Go to section 12.3**

Yes      If using Gillette resources, please contact:

[name], PT  
Research Administration Manager

Gillette Children's Specialty Healthcare  
[contact]/[contact]/[[contact]](mailto:[contact])

**12.2.4 Will this research use Magnetic Resonance (MR) Devices housed at the Center for Magnetic Resonance Research (CMRR) facilities?**

No      **Go to section 12.3**

Yes      **Review and approval by the [CMRR Safety Committee](#) is required prior to IRB submission.**

CMRR users must submit the completed CMRR Device and Safety Review form to the CMRR prior to submission of their IRB application. A draft copy of the IRB application must be included along with the CMRR Device and Safety Review form for CMRR Safety Committee review. Documentation of approval by the CMRR Safety Committee will be provided to the researcher to include with the IRB application submission.

**Section 12.3 PAYMENT FOR RESEARCH RELATED SERVICES**

**12.3. 1 Does the protocol require the use of tests, procedures, clinic space, clinic visits, professional fees, lab services, pharmacy services, or hospital services in order to answer the research question?**

No      **Go to section 12.4**

Yes

**12.3.2 Will subjects or a third party be charged for research related procedures?**

No

Yes      **Explain:** These are standard of care and as such are charged to the patient as per routine  
**Provide written documentation from the FDA to charge for investigational products.**

### 12.3.3 Will Services be provided by Fairview Health Service or U of M Physicians?

No

Yes Provide TASCs Number:

Provide a copy of the TASCs billing grid noting whether the study does or does not meet Medicare criteria for a Qualifying Clinical Trial.

Applications will not be assigned for review until the TASCs information is submitted.

## CLINICALTRIALS.GOV REGISTRATION

### Important Information about [clinicaltrials.gov](http://clinicaltrials.gov) registration

#### Resources available, penalties for failure to register and publication requirements

Potential risks associated with failure to register with [clinicaltrials.gov](http://clinicaltrials.gov):

- Loss of funding (National Institute of Health)
- Financial penalty levied against the PI
- Denial of publication (ICMJE)
- Denial of payment to healthcare providers.

Section 801 of the Food and Drug Administration Amendments Act (FDAAA 801) establishes penalties for Responsible Parties who fail to comply with registration or results submission requirements. Penalties include civil monetary penalties and, for federally funded studies, the withholding of grant funds.

The International Committee of Medical Journal Editors (ICMJE) defines a clinical trial as any research project that prospectively assigns human subjects to intervention or concurrent comparison or control groups to study the cause-and-effect relationship between a medical intervention and a health outcome. Medical interventions include drugs, surgical procedures, devices, behavioral treatments, process-of-care changes, and the like.

Research projects that meet the ICMJE definition may not be accepted for publication if they are not registered in a registry that is electronically searchable and accessible to the public at no charge. For more information on this requirement see <http://www.icmje.org> Note that retrospective registration of projects is not allowed.

Additionally, healthcare providers are required to include the [clinicaltrials.gov](http://clinicaltrials.gov) number on all claims during the time period the patient participates in the study.

**The Clinical and Translational Science Institute (CTSI) will assist University of Minnesota investigators to comply with the registration requirement. Complete the section below to document status or determine if registration is required. Applications submitted without a [Clinicaltrials.gov](http://clinicaltrials.gov) registration number (either received or pending) will be forwarded to the CTSI for review.**

## Section 12.4 CLINICALTRIALS.GOV REGISTRATION DETERMINATION

### 12.4.1 Is this project registered with [clinicaltrials.gov](http://clinicaltrials.gov)?

No **Go to 12.4.2**

Yes **Clinicaltrials.gov registration number:**pending  
 If registration is pending enter “pending” in the space provided.

**Section complete. Go to Section 12.5**

Does this project meet the [Food and Drug Administration Amendments Act \(FDAAA\)](#) definition of “applicable clinical trial”? Applicable clinical trials generally include controlled, clinical investigations of drugs and biologics; and controlled trials of devices that include health outcomes, including pediatric postmarket surveillance.

**12.4.2 Is registration with clinicaltrials.gov required?**

No **The PI understands the registration requirements and the consequences, as described above, of failure to register if applicable.** CTSI will review this application for concurrence with the PIs decision. CTSI will contact the PI and the IRB to confirm registration requirement. If registration is required, the PI may request assistance with this process from CTSI. **Go to Section 12.5**

Unsure **CTSI will contact the PI and the IRB with a determination regarding the registration requirement. If registration is required, the PI may request assistance with this process from CTSI. Go to Section 12.5**

Yes **Answer the questions below to determine who (either the PI or other entity) is responsible for registration with clinicaltrials.gov**

Is this study initiated by a University of Minnesota investigator?  No  Yes – registration by PI required.

Is this study federally sponsored and the University of Minnesota is the only study site OR the study’s coordinating center?  No  Yes – registration by PI required.

Is a University of Minnesota investigator the holder of an Investigational New Drug (IND) application for the test article OR it has been determined the proposed use of the test article is IND exempt?  No  Yes – registration by PI required.

Is a University of Minnesota investigator the holder of an Investigational Device Exemption (IDE) for the device being studied OR a non-significant risk (NSR) determination has been made for the device being studied?  No  Yes – registration by PI required.

**If registration is required, the registration number must be provided before final IRB approval is granted. Email [[contact]](mailto:[contact]) for additional information and registration assistance. CTSI will evaluate all applications not registered with clinicaltrials.gov.**

**Section 12.5 SCIENTIFIC ASSESSMENT**

Research involving human subjects must be reviewed for sound scientific design prior to review by the IRB committee. Documentation of scientific assessment including the content of the review must be provided before the project will be reviewed by the IRB. Scientific assessment is not required for new studies that meet the federal criteria for expedited review. If a study is submitted for expedited review but is determined by the IRB to NOT meet the criteria for expedited review, then scientific peer review will be required before IRB review.

**12.5.1 Has the IRB scientific assessment requirement been met?**

N/A **Project qualifies for expedited review. Sections 12.5, 12.6 and 12.7 are not required if expedited review eligible. GO TO Section 13 Additional Staff.**

 Yes	Indicate below how the requirement has been met	Required supplemental materials
	 Option 1 Reviewed by a federal funding agency (National Institutes of Health, National Science Foundation, etc.) employing peer review mechanisms for awarding of funding.	
	 Option 2 Reviewed by a nationally based non-federal funding agency (March of Dimes, American Academy of Pediatrics, etc.) employing peer review mechanisms for awarding of funding	Note: industry-sponsored clinical trials designed by the sponsor with or without external consultants do not satisfy this criterion for independent peer-review.
	 Option 3 Reviewed by locally constituted mechanisms using peer review for awarding of funding, or for permission to use resources: Cancer Protocol Review Committee (CPRC); CTSI funded pilot awards; Vikings; departmental peer review etc.	Attach the review and the signed form documenting that departmental or collegiate peer review of the research protocol has been performed.
 Option 4	Reviewed by HRPP facilitated Scientific Assessment committee	Submit approval notification with application.

**Section 12.6 DATA AND SAFETY MONITORING PLAN**

A data and safety monitoring plan (DSMP) is meant to assure that each clinical investigation has a system for oversight and monitoring of the conduct of the clinical investigation. This oversight is intended to ensure the safety of the participants and the validity and integrity of the data. A DSMP should be commensurate with the risks.

A DSMP can be as simple as the investigator reporting adverse event information to the IRB. A DSMP can be as complex as having a Data and Safety Monitoring Board.

A DSMP can include clinical trial monitoring. Clinical trial monitoring refers to the methods used to oversee the conduct of, and reporting of data from, clinical investigations including appropriate clinical investigator supervision of study site staff. Monitoring activities include communication with the investigator and the study site staff; review of the study site’s processes, procedures, and records; and verification of the accuracy of the data.

**12.6.1 In addition to the Principal Investigator, are there other DATA monitoring entities responsible for this function? Select all that apply.**

- No, the PI is the only entity monitoring DATA.**
- Yes**
  - A review entity will provide ongoing DATA monitoring**
  - Clinical and Translational Science Institute (CTSI)**
  - Data coordinating center or project principal investigator (multi-center studies)**
  - Commercial sponsor, contract research organization (CRO)**

Other:

**12.6.2 In addition to the Principal Investigator, are there other SAFETY monitoring entities responsible for this function? Select all that apply.**

**No, the PI is the only entity monitoring SAFETY.**

**Yes Select all below that apply**

**A Data Safety Monitoring Board (DSMB) will be appointed.**

**When established, the list of the DSMB members including their affiliation and credentials and the DSMB charter must be submitted to the IRB. A description of the DSMB must be provided with the application.**

A Data and Safety Monitoring Board (DSMB) is an independent group of experts that advises the study investigators. Primary responsibilities of a DSMB are to 1) periodically review and evaluate the accumulated study data for participant safety, study conduct and progress, and, when appropriate, efficacy, and 2) make recommendations concerning the continuation, modification, or termination of the trial. The DSMB considers study-specific data as well as relevant background knowledge about the disease, test agent, or patient population under study.

The DSMB reports should be provided to the IRB as they are received.

**Medical Monitor**

**Cancer Center Data Safety Monitoring Council**

**Other, describe:**

### Section 12.7 DATA AND SAFETY MONITORING RESPONSIBILITIES

Data to be monitored	PI	Review entity	DSMB/other	Unassigned
Study Safety (e.g., collection, reporting, and management of AEs, SAEs, and other study risks).				
Data Accuracy & Quality Assurance (e.g., data collection, entry, transmission and analysis).				
Trial Management (e.g., site coordination, enrollment and population distribution).				
Regulatory Issues (e.g., SAE reporting, IRB Actions, disclosures of conflict of interest).				
Interim Analysis.				

**It is the investigator's opinion that this protocol does not require a data safety monitoring plan. Provide justification:**

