#### 2.3 Explain how the study design and methods will answer the research question.

This is a double blinded randomized study. All patients will receive one form of local anesthetic pain relief either from TAP or infiltration. Patients will be randomized to one of two study arms in a double-blinded, placebo controlled study. All patients will receive a TAP infiltration and all patients will receive infiltration into the incision. In one arm the TAP infiltration will contain 10 mL of 0.25 % bupivacaine with epinephrine injected followed by 20 mL of a 50:50 mixture of liposomal bupivacaine and normal saline. This will then be repeated on the contralateral side. In the same arm the surgeon infiltration into the incision will consist of 10 ml of normal saline per port site, 5 ml prior to incision and 5 ml prior to closure at each port site.

In the second arm the bilateral TAP infiltration will consist of 30 mL of normal saline per side. In the same arm the surgeon infiltration will consist of 10 mL of 0.25% bupivacaine per port site. The surgeon infiltration will consist of 5 ml of 0.25% bupivacaine prior to incision and 5 ml of 0.25% bupivacaine prior to closure at each port site.

A TAP infiltration is an injection of local anesthetic under the covering of the transversus abdominis muscle layer which provides effective post operative analgesia. This layer is found using an ultrasound, which is a beam of high frequency sound that allows one to visualize images in the body. Then using this ultrasound we can see our needle as it pierces the covering of the transversus abdominis muscle layer and watch as the local anesthetic is infiltrated into this plane. This is done on both sides of the abdomen to provide analgesia to the skin, muscle, and facial layers of the abdomen. This is currently standard of care at our institution and will be performed within one hour of surgical incision. The injection will consist of 10 mL of 0.25% bupivacaine with epinephrine followed by 20 mL of liposomal bupivacaine saline mixture or 10 ml of saline followed by 20 ml of saline and then repeated on the contralateral side.

Surgical Infiltration of the study solution will be performed both prior to incision and at the end of surgery just prior to closure of incisions. At each time, the surgeon will inject 5 mL of 0.25% bupivacaine into each of the port site

incisions.

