Investigational Drug Service (IDS) pharmacy will be charged with the blinding of medications vs. saline for these procedures.

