**2.4 What will the subjects be asked to do solely for the purpose of this research?**

Subjects will be asked to be randomly assigned to receive either a TAP with liposomal bupivacaine or infiltration with bupivacaine. They will also be asked to answer questions at various time points related to their pain, answer a survey on their quality of recovery. They will also be asked to allow the research staff to access their medical chart to obtain information about their pain medication use, complications, demographics, and time of discharge.

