**If statement B is selected, answer the questions 6.1.1. – 6.1.3 below**

**6.1.1 Explain how the researcher has legitimate access to these records.**

The PI is a surgeon at the University of Minnesota

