**6.1.2 Identify who will make initial contact with potential subjects.**

The PI or Co-Investigators

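### Does ticking the PI for interim analysis in Section 12.7 put the double blind or the type I error at risk?

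*Protocol*

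**What the plan says.** Section 12.7 of the Protocol is a table with five printed rows and four columns: PI, review entity, DSMB/other, and unassigned. Every row is ticked for the PI and for nobody else. Three rows matter here:

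- "Interim Analysis";
- "Trial Management (e.g., site coordination, enrollment and population distribution");
- data accuracy and quality assurance ("e.g., data collection, entry, transmission and analysis").

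On blinding, Section 2.3 states: "Patients will be randomized to one of two study arms in a double-blinded, placebo controlled study". It also says who does it: "Investigational Drug Service (IDS) pharmacy will be charged with the blinding of medications vs. saline for these procedures".

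On the PI's role, Section 6.1.1 says "The PI is a surgeon at the University of Minnesota", and Section 6.1.2 gives first contact with patients to "The PI or Co-Investigators". On outcomes, Section 2.4 says of the patients: "They will also be asked to answer questions at various time points related to their pain". They also complete a quality-of-recovery survey.

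Section 4.2 sets enrolment at 60. The Protocol gives no significance level, no number or timing of looks, and no stopping boundary.

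**The concern.** Whoever sees results by arm during recruitment should not also influence who is enrolled, how patients are handled or how outcomes are collected. Section 12.7 appears to put all of this with one person, who is also a surgeon at the site, in a trial where surgeons give one of the two blinded injections (Section 3.3). Columns for a review entity, for a DSMB and for leaving the task unassigned were available and were not used. No sentence confines the PI to pooled data.

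Two things would be at stake. First, a PI who knew the emerging difference might, without meaning to, change recruitment or conduct, and pain and recovery are self-reported outcomes that staff behaviour can affect. Second, if an unplanned look could end the trial or support an efficacy claim with no adjustment, the false-positive rate would exceed its nominal level.

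**Working it through.** **Step 1. What the table assigns.** Section 12.7 concerns monitoring responsibilities, and its first column lists what is to be monitored. A tick therefore says who answers for an area, not who carries out every task in it. Other sections show the work is shared:

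| Task | Section 12.7 | Who does it elsewhere in the Protocol |
|---|---|---|
| Approaching patients | PI | PI or co-investigators (6.1.2) |
| Consent on the day of surgery | PI | After discussion with the anesthesiologist co-PI (9.1) |
| Access to charts for data | PI | Trained research personnel (3.3) |
| Blinding of the injections | no row | Pharmacy (2.3) |

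The PI alone holds monitoring responsibility. It does not follow that the PI alone runs enrolment and data collection.

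**Step 2. Whether a look is planned.** Apart from the printed row in Section 12.7, the Protocol does not describe an interim analysis of this trial. Sections 2.3 (design), 4.1 and 4.2 (numbers) and 12.6 (monitoring) give no date, number of patients, comparison or stopping criterion for one.

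**Step 3. Who could see results by arm.** Section 2.3 declares the trial double-blinded and gives blinding to the pharmacy. No section hands the codes to the PI or provides for releasing them early. The ordinary reading is that the declared blind applies to any review made while the trial is running.

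**Step 4. What harm would require.** Three things, none of them stated: a look takes place, it is by arm, and the PI sees it unblinded. Type I error inflation needs a fourth, namely that the look can stop the trial or support a claim without adjustment.

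**Step 5. Size if all of that happened.** The Protocol has no figure to reproduce. Inputs: 60 patients (Section 4.2); a two-sided 5% level, critical value 1.96 (assumed); one look after n patients (assumed). Under the null hypothesis the interim and final statistics Z1 and Z2 are standard normal with correlation √(n/60), and the overall error is

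P(|Z1| > 1.96 or |Z2| > 1.96) = 1 − P(|Z1| ≤ 1.96 and |Z2| ≤ 1.96).

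| Look after | n/60 | Correlation | Error if the look can stop or claim, unadjusted | Error if it cannot |
|---|---|---|---|---|
| 20 | 0.333 | 0.577 | 0.0883 | 0.0500 |
| 30 | 0.500 | 0.707 | 0.0831 | 0.0500 |
| 40 | 0.667 | 0.816 | 0.0770 | 0.0500 |
| 45 | 0.750 | 0.866 | 0.0734 | 0.0500 |

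A separate simulation of 2,000,000 trials with one look at half the data gave 0.0832, which agrees. The right-hand column is the one that fits the Protocol as written, because it contains no rule for stopping or claiming early. A pooled or safety-only look would also leave the error at 5%.

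**Step 6. What a by-arm look would disclose.** A summary by coded arm reveals no individual's allocation. Even decoded results on completed patients would not reveal the next patient's pharmacy-blinded assignment, and the patients who report pain would still be blinded. What could leak is the trend, which might affect conduct, but only indirectly.

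**The case for a change.** The strongest case for a change is that the tick is a positive choice in the document, not a silence left for the statistical analysis plan. *Unassigned* was available and would have suited a trial with no interim analysis. The PI is a surgeon, and nothing excludes the PI from giving the infiltration to trial patients. Section 11.1 discloses that one investigator, whose role is not shown, has speaker, consulting and research-funding ties, a further reason to keep any by-arm look independent. The remedy is also cheap: one cell and one sentence.

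Some of this stands. The row names an owner for a task the Protocol never defines, and no text expressly bars releasing the codes. Knowledge of a trend can affect conduct even when individual allocations stay hidden. If a by-arm look were intended, it should go to someone with no part in recruitment, treatment or outcome collection, with its timing and boundary set beforehand.

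The rest does not carry the point. With the PI ticked in every row of a single-centre, department-funded study, the interim tick reads as a default. Section 12.6 asks for oversight in proportion to risk, and at the simple end it accepts adverse-event reporting by the investigator. Whether a look is pooled or by arm, who sees it and what boundary applies are details that commonly sit in a statistical analysis plan. Moving the tick might not help either: the form does not define *Unassigned*, which could be taken to mean that nobody covers the task.

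**Conclusion.** No change to the plan is needed. The tick is as described, but carrying out the Protocol as written, with its declared double blind, pharmacy blinding and no scheduled look, leaves the comparison sound. The type I error inflation attributable to the plan is zero; the range of 7.3% to 8.8% belongs to a different trial, one with an unadjusted look that could stop it or support a claim.

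A sentence saying that no between-arm look is planned and that ongoing review uses pooled, blinded data would be a harmless clarification. It would record the natural reading rather than alter the design, so it is optional.

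This conclusion rests on two assumptions: that the double blind covers any review during the trial, and that the printed row does not signal an undisclosed by-arm look. Pages after Section 12.7 could not be checked. If a by-arm look by the PI were in fact intended, the conclusion would no longer hold.
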